ClinicalTrials.gov Data Entry Cover Sheet

Protocol ID: 22811 **Clinical Trials.gov ID:** NCT05988398

Project Title: Preventing Commercial Sexual Exploitation of Children (Project LIVE)

Principal Investigator: [name], University of Nebraska-Lincoln

Statistical Design and Power

Power Analyses

Aim 1a. N/A

Aim 1b. There is no “magic bullet” for sample size in qualitative research.¹²⁷⁻¹²⁹ The sample size proposed for focus groups is consistent with other research conducted by the PI and Co-I ([name]) that should allow for saturation (i.e., the collection of new data does not produce additional insights).¹³⁰ However, the sample size may be adjusted until data saturation is achieved.¹³⁰

Aim 1c. N/A

Aim 1d. Power analyses to support the sample size for the measurement development study (for multi-item measures) are based on prior simulation work.¹³¹ The proposed sample size of $n=878$ baseline surveys from youth will be utilized by splitting the sample in half to conduct exploratory factor analysis (EFA) and confirmatory factor analysis (CFA), each with 439 youth. A sample size of 439 youth is adequate for implementing factor analyses using structural equation modeling approaches and provides power ($> .80$) to estimate two factor models, five manifest indicators each, nonnormal data, and factor loadings = .80.

Aim 1e. Regarding qualitative data, see narrative above for Aim 1b. Also, power analyses were not conducted for descriptive data (e.g., frequencies of the number of sessions attended, extent to which sessions were delivered with fidelity). Regarding student survey data collected as part of the OPT, we will examine changes in intermediary outcomes (see Figure 1) over time given that there will likely not be a sufficient window of time to see changes in behavioral primary and secondary outcomes at the immediate post-test which will happen within a few days to a week or two following the ending of the programming. For the exploratory program impact analysis on intermediary outcomes (Figure 1), a sample size of $n=878$ (approximately .5 assignment rate to condition), will provide adequate power (.80; $\alpha=.05$) to detect a minimum effect size (MDES) $d=.20$ as determined by G-Power analysis of covariance (ANCOVA) routine.

Aim 1f. N/A

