Aim 2a. Power analyses to support the sample size for the effectiveness analyses for our primary, secondary, and intermediary outcomes (see Figure 1) were conducted using G-Power 3.1. Power was set to .80 and $\alpha=.05$. Component A of the study will provide incidence rates which will be used to recalculate power prior to the implementation of Component B. For the purposes of this proposal, we calculated the MDES based on the proposed sample size. For the primary outcome of CSEC perpetration, there are no reliable incidence estimates in the literature on which to draw. With a sample size of 7,241 students enrolled, assuming conservative minimum incidence rates of CSEC perpetration of 1% to 5% (although we hypothesize it will be higher), we have power to detect an MDES difference between conditions, odds ratio (OR)=.49 to .75, respectively. Similarly, for secondary outcomes of CSEC victimization, we estimated a range of incidence rates from a conservation 5% to 50%+ based on literature discussed following for other types of victimization^{96, 132, 133} as well as rates of CSEC youth at increased risk (e.g., system involved, homeless)¹⁸⁻²⁰, which will be present in our sample based on DMPS data, we have the power to detect an MDES difference between conditions, odds ratio (OR)=.75 to .88, respectively. For secondary outcomes of TDV/SV perpetration and victimization, given past 12- months incidence rates¹³² (from nationally representative data from youth) of 63% for perpetration (of any type of TDV) and 69% for victimization (of any type of TDV), we have power to detect an MDES difference between conditions, odds ratio (OR)=.88 to .89. For sub-types of TDV (past 12-month incidence rates: physical victimization: 18%; sexual victimization: 18%; psychological victimization: 66%; physical perpetration: 12%; sexual perpetration: 12%; psychological perpetration: 62%)¹³², we have power to detect an MDES difference between conditions, odds ratio (OR)=.83 to .89, respectively. For the secondary outcome CSEC bystander action and opportunity and intermediary outcomes (i.e., knowledge, valuing of self and others, healthy relationship skills, bystander efficacy, perceptions of school social norms, prevention conversations with school personnel), the ANCOVA routine suggested power (.80) to detect a small difference between groups (MDES $d=.06$).

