Aim 1e. Regarding qualitative data, see narrative above for Aim 1b. Descriptive analyses will be used to gauge things such as the average number of sessions attended, the extent to which sessions were delivered with fidelity, etc. Regarding pre- to post- changes in intermediary variables, we will use analysis of covariance, including the baseline measurement of the outcome as a covariate, the condition as the independent variable, and the post-test measure of the outcome as the dependent variable. The analysis will examine differences between conditions to determine preliminary program impact and effect sizes. Maximum likelihood estimation will be used to account for missing data in the analyses. Classroom will be used as a cluster variable to adjust the standard errors for nesting.

Aim 1f. N/A

Aim 2a and 2b.

Preliminary Analyses.

We will guard against differential attrition across experimental conditions. We will track and examine if attrition rates differ for the experimental groups. We expect similar rates of attrition across experimental groups. Furthermore, we will use data from all enrolled cases, who all have baseline data based on our design in our analyses to limit the bias introduced by missing data. Missing data assumed to be at least MAR will be dealt with as a function of the data analytic process through maximum likelihood estimation (ML), which makes use of all available data and does not require deletion of incomplete cases.

Outcome Analyses (Aim 2a).

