We will test the hypotheses related to examining effectiveness of participation in the RTS in leading to reductions in CSEC perpetration (primary outcome), as well as reductions in CSEC victimization and TDV and SV victimization and perpetration and increases in bystander intervention in CSEC situations (secondary outcomes). To improve the rigor of analyses for Aim 2a, we will use propensity-score analysis to reduce the impact of selection bias, and latent constructs, when possible, to reduce measurement error, reduce paths and variables, and increase statistical power (MacCallum et al., 1996). This approach produces rigorous estimates of causal effects within the context of quasi-experimental designs when random assignment is not possible by controlling confounders, including selection effects¹⁴⁴. This approach will use four analytic steps: (1) estimate propensity scores in a separate analysis, (2) use the propensity scores to adjust for confounding, (3) assess balance, and (4) estimate the propensity score-adjusted treatment effects (Lanza et al., 2013). In step 1, to estimate the propensity score, we will consider all pertinent confounders and covariates (see Measurement Table 3). This step will use logistic regression of condition on the potential confounders to obtain each student's propensity score. All measured confounders that are predictive of selection into the experimental conditions and the outcomes will be included in the propensity model. Standardized mean differences in covariate values across treatment and comparison conditions will be used to determine the final set of confounders to include in estimating the propensity score. In step 2, an initial treatment effect model is estimated that adjusts for confounding using the propensity score. We will use inverse probability weighting (IPTW) to adjust for confounding. The standardized mean differences between experimental groups are computed on the weighted sample included the IPTW-adjusted propensity score (Step 2). If IPTW does not provide optimal balance, then other methods will be considered (e.g., matching). Then Step 3 is used to determine balance on the potential confounders included in the propensity score across the experimental groups. The goal is to determine whether there are any differences remaining on the confounders between experimental groups (balance = standardized mean differences $< |0.2|$ after adjustment). Confounders will be adjusted and the propensity score model (Step 1) will be re-estimated until balance is reached. Once balance is determined, the outcome analysis will be conducted in Step 4 via SEM. The experimental effect of interest will be the Average Treatment Effect (ATE), which is the population-level average effect of condition on the primary and secondary outcomes as detailed in the logic model. The effects of interest quantified are differences between experimental conditions at post-test and follow-up on outcomes (for continuous measures), the propensity score as a covariate. These effects indicate whether the outcomes in the experimental condition differ significantly from those in the comparison condition. At post-test and follow-up, we expect the difference between the experimental conditions to be significantly greater than zero, reflecting better outcomes for those in the RTS program as compared to those in the wait-list condition, after adjusting for the

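### The only attrition diagnostic for Aim 2a compares dropout rates between arms, and the missing-data method as written gives limited protection if different kinds of students leave each arm

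*SAP*

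**What the plan says.** **Diagnostic.** SAP, Proposed Analyses, Aim 2a and 2b, Preliminary Analyses: "We will track and examine if attrition rates differ for the experimental groups. We expect similar rates of attrition across experimental groups". Neither document plans a comparison of leavers' baseline characteristics by arm, a model of dropout, auxiliary variables, or a sensitivity analysis for data not missing at random.

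**Missing-data method.** The same paragraph goes on to commit to analysing every enrolled student, all of whom have baseline data, by maximum likelihood (ML) on the assumption that missingness is at least MAR.

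**Adjustment.** Under Outcome Analyses (Aim 2a), Step 1 models condition on confounders taken from Measurement Table 3. Step 2 applies inverse probability weighting (IPTW). On Step 3 the SAP says: "The goal is to determine whether there are any differences remaining on the confounders between experimental groups", with a threshold of 0.2 on the standardized mean difference (SMD). It does not say whether this is checked at baseline or among students who still have outcome data. The outcome model names condition, propensity score and school, with logistic regression for categorical outcomes and standard errors adjusted for classroom. The baseline measure of the outcome is a named covariate only for the Aim 1e pilot ANCOVA.

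**Population.** Power Analyses, Aim 2a, expects the sample to include higher-risk youth; in setting victimization rates it refers to "rates of CSEC youth at increased risk (e.g., system involved, homeless" and similar groups.

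**The concern.** Two arms can lose the same percentage of students and still lose different students. If high-risk students leave one arm more often, and low-risk students leave it correspondingly less often, the rates agree and the diagnostic reports nothing. The students with outcomes are nevertheless no longer comparable.

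ML under MAR could repair this, but only if the variables that drive dropout are in the model. In a logistic model with condition, propensity score and school, a student whose outcome is missing contributes almost no information on the treatment effect. The propensity score does not fill the gap: it predicts condition, so a risk factor that is balanced between arms at baseline gets little weight in it, however strongly that factor predicts dropout.

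CSEC perpetration is the primary outcome, it is assumed to be rare, and the comparison is not randomised. A modest shift in who remains could be read as a programme effect, or could hide one.

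**Working it through.** **The plan's own figure.** Inputs from Power Analyses, Aim 2a: "With a sample size of 7,241 students enrolled"; "assuming conservative minimum incidence rates of CSEC perpetration of 1% to 5" per cent; power .80 and alpha .05. The result stated is "we have power to detect an MDES difference between conditions, odds ratio (OR)=.49 to .75, respectively". Allocation is given as about .5 for the pilot only; I assume 1:1 here, so about 3,620 per arm. A two-proportion calculation solved for the OR gives:

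- one-sided alpha .05: OR .494 at 1% and .751 at 5%, matching the SAP;
- two-sided alpha .05: OR .440 and .722, which does not match.

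The SAP does not state sidedness. The calculation uses the enrolled number, and no attrition figure is given anywhere.

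**Illustration: inputs (assumed unless marked).** No true effect; overall incidence 5% (top of the SAP's range); 10% of students high-risk with 25% incidence, so low-risk incidence = (.05 − .10 × .25)/.90 = .0278; 80% retained in each arm; N = 7,241 (SAP), 1:1; two-sided .05 Wald test.

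1. RTS keeps 60% of high-risk students. To retain 80% overall it keeps (.80 − .10 × .60)/.90 = 82.2% of low-risk students. The wait-list keeps 80% of both.
2. Incidence among RTS responders = (.06 × .25 + .74 × .0278)/.80 = .0444. Wait-list: .0500.
3. OR = (.0444/.9556)/(.0500/.9500) = .884, with a true OR of 1.
4. Responders per arm = 3,620.5 × .80 = 2,896. SE(log OR) = sqrt[1/(2,896 × .0444) + 1/(2,896 × .9556) + 1/(2,896 × .05) + 1/(2,896 × .95)] = .124.
5. z = .1236/.124 = 1.00, so the rejection rate is Φ(1.00 − 1.96) + Φ(−1.00 − 1.96) = 16.9%.
6. The SAP adjusts for classroom. With an assumed design effect of 1.5 to 2, z falls to .81 to .70 and the rate to 13% to 11%.

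| RTS v wait-list retention of high-risk students | OR | Rejection rate (no clustering) |
|---|---|---|
| 70% v 80% | .942 | 7.8% |
| 60% v 80% | .884 | 16.9% |
| 60% v 90% | .835 | 31.3% |

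Swapping the arms in the middle row gives OR 1/.884 = 1.13.

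**Do the planned adjustments remove it?** In 300 simulated trials of the middle row, the propensity score as covariate gave OR .88 and IPTW gave .88. IPTW multiplied by arm-specific inverse response probabilities gave .99 to 1.00, and baseline risk in the outcome model gave 1.00. The SD of the log OR was about .12 with or without response weights. The mean gap in attrition rate between arms was .0075.

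**Would a balance check at 0.2 see it?** The high-risk share among responders is .06/.80 = .075 v .10, so SMD = −.025/sqrt(.10 × .90) = −.08. It would pass.

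**Second set of assumptions.** 20% of students high-risk (17% v 2% incidence), 20% dropout per arm; 40% of high-risk and 15% of low-risk students leave RTS, and 20% of each leave the comparison arm. Expected OR = .84. In 1,000 simulated trials: OR .85 with type I error about 27% without baseline risk in the model, and OR 1.01 with about 6% with it. A test of the attrition rates rejected in about 4% of trials.

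**Dropout driven by the outcome itself.** If 40% of RTS perpetrators leave and 20% leave overall in each arm, non-perpetrators are retained at (.80 − .05 × .60)/.95 = .811, so OR = .60/.811 = .74. Adjusting for baseline risk does not change this.

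**The case against.** The strongest reply is that the SAP does have a second safeguard: ML under MAR on every enrolled student, offered expressly to limit missing-data bias. That stands. A reader might infer that the rate comparison is the only protection and that nothing later can repair selective dropout; the same paragraph contradicts that. What remains is that ML works through the variables in the model, and those named for Aim 2a do not include the baseline outcome or predictors of dropout.

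Table 3 is not in the documents, so baseline CSEC perpetration or risk status may enter the propensity score. Also true, and if those variables differ between arms at baseline, the score would carry some of their information. But a score built to predict condition does not in general adjust for dropout that differs by arm.

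The SAP does not say whether post-test and follow-up are modelled jointly. If they are, a student seen at post-test but not at follow-up would contribute something. A student missing both would not.

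Finally, every scenario is assumed. The documents give no dropout rate, no risk share and no direction. With clustering the mildest case falls to about 6% to 7%, close to nominal, and an OR of .88 is well short of the SAP's detectable .75 at 5% incidence. This limits the size of the point, not its logic.

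**Conclusion.** The point holds as a gap in the plan that should be closed. The only attrition diagnostic cannot detect different kinds of leavers at equal rates, and protection otherwise rests on MAR given condition, propensity score and school, which the plan never examines.

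In the central illustration a true OR of 1 appears as about .88, with a false-positive rate of about 17% ignoring clustering and 11% to 13% with a design effect of 2 to 1.5. This rests on assumed retention, risk share and incidence, on 1:1 allocation, and on baseline risk being outside the outcome model.

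A reader might go further and conclude that the RTS effect will be biased, or biased in favour of RTS. The documents support neither. Bias arises only if dropout depends, differently by arm, on something outside the model or on the outcome itself, and reversing the pattern would hide a benefit (OR 1.13).

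**What to change.** Amend the SAP as follows.

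1. **Preliminary Analyses.** At each wave, report baseline characteristics by arm (SMDs) among students with outcome data, beside the attrition rates. Do not treat 0.2 as a pass mark on its own, since an SMD of −.08 accompanied the OR of .88 above.
2. **Step 4.** Include the baseline measure of the outcome and baseline predictors of dropout as covariates or auxiliary variables in the ML model. Alternatively, multiply the IPTW by inverse response probabilities fitted separately by arm. Either is adequate. Say which is used: auxiliary variables or weights keep the population-average effect that the SAP targets, whereas covariates in a logistic model give a conditional odds ratio.
3. **Assumption and sensitivity.** State that either approach still assumes MAR given those variables, and add a simple non-MAR analysis for CSEC perpetration, for example varying the assumed incidence among leavers by arm.

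The cost is SAP wording and some extra analysis, with slightly wider standard errors or more variable weights. Every enrolled student has baseline data, so no new students are needed. The documents do not show which baseline variables are collected, so the models should use those available.

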
propensity score. For categorical variables, logistic regression will be used to examine differences in prevalence by condition. The experimental condition is the independent variable in these models. Multilevel modeling is not possible given the small number of schools; thus, school will be included as a covariate. Classroom will be used as a cluster variable to adjust the standard errors for nesting. Models for Step 4 will be evaluated for overall model fit via χ^2 statistic, RMSEA :s .08, SRMR :s .10, and CFI \geq .90. We will evaluate our hypotheses across several indicators, including significance (p), confidence intervals, and the standardized difference between groups (d), as well as the directionality of included path coefficients, and odds ratios.

Mediation and Moderation Analyses (Aim 2b).

We will assess mediators (e.g., perceptions of norms intolerant of CSEC) and demographic moderators (e.g., gender) of program effectiveness, including the propensity score and school as covariates in all models. To test for mediation, we used the product of coefficients method using bias-corrected bootstrapping with 1000 resamples to calculate the confidence intervals¹⁴⁵ (MacKinnon, 2012). For our moderators (e.g., age, gender, racial groups, sexual orientation), we will estimate structural equation multiple group models, first allowing estimation of the path coefficients to vary freely across groups, and then constraining paths to be equal when a structural path coefficient of interest was significant for one group and not the other group. We will conduct model comparisons using the chi-square (χ^2) difference test (i.e., χ^2 , $p < .05$ indicating moderation).

Aim 2c. Descriptive statistics will be used to examine the extent to which sessions were delivered with fidelity. Process observations will be analyzed using thematic analysis as described above for Aim 1b.

Aim 2d. Descriptive statistics will be used to examine the frequency of responses to close-ended questions (e.g., To what extend did you like the session today?). Open-ended questions will be analyzed using thematic analysis as described above for Aim 1b.

Aim 2e. Interview data will be analyzed using thematic analysis as described above for Aim 1b.

Aim 2f. The purpose of this aim is to determine costs associated with the program implementation to inform future economic evaluation of the RTS. The process for documenting costs are described in Section C.18.

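### The Aim 2a detectable odds ratios count all 7,241 enrolled students, but in the logistic regression planned for binary outcomes a student with no outcome adds nothing on the treatment effect.

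*SAP*

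**What the plan says.** Four statements in the SAP bear on this.

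- **Power Analyses, Aim 2a.** The primary outcome is sized "With a sample size of 7,241 students enrolled", with power .80 and alpha .05. For control incidences of 1% and 5% the minimum detectable effect is "odds ratio (OR)=.49 to .75, respectively". For victimization, at 5% to 50% or more, it is "odds ratio (OR)=.75 to .88, respectively". Power is to be recalculated before Component B from the incidence rates seen in Component A. Retention is not mentioned.
- **Preliminary Analyses (Aim 2a and 2b).** Attrition is expected, at similar rates in the two groups, and will be compared between them. The text adds that "we will use data from all enrolled cases, who all have baseline data", and that maximum likelihood "makes use of all available data and does not require deletion of incomplete cases".
- **Outcome Analyses (Aim 2a), binary outcomes.** For categorical variables, "logistic regression will be used to examine differences in prevalence by condition". The propensity score and school are covariates, and standard errors are adjusted for classroom.
- **Outcome Analyses (Aim 2a), Step 4.** The outcome analysis is placed in a structural equation framework, with effects at post-test and follow-up. No joint model of the two waves, auxiliary variables or imputation is written down for binary outcomes.

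**The concern.** Maximum likelihood uses partly observed records only through variables that the model treats as random. In a regression of one binary outcome on observed covariates, the only random variable is that outcome. A student who lacks it has nothing to contribute, so holding that student's baseline data does not by itself keep the student in the treatment comparison.

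Two things are at stake. The stated power for a rare primary outcome refers to more students than will supply that outcome. And post-test answers, the most recent information on a student lost before follow-up, are not used to make missing at random more plausible.

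**Working it through.** **1. Contribution of a student with a missing outcome.** With fitted probability p, an observed student contributes y·log p + (1 − y)·log(1 − p) to the log-likelihood. If y is missing, summing over its two values gives log[p + (1 − p)] = log 1 = 0. An inverse-probability weight times 0 is still 0. In simulated data with 20% of outcomes missing at random, the information-based standard errors with those rows kept equalled those of the complete-case fit. Information on the treatment effect was 80% of the full-sample value. Such students do still inform the propensity model in Step 1.

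**2. Reproducing the stated figures.** Inputs from the SAP: N = 7,241, power .80, alpha .05, control incidence 1% and 5%. Assumed: 1:1 allocation, since about .5 is given only for the open pilot trial. Sidedness is not stated, so both were tried. There is no allowance for clustering or weighting.

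p₂ = p₁·OR / (1 − p₁ + p₁·OR), n = N/2 per arm, p̄ = (p₁ + p₂)/2

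Power = Φ{[(p₁ − p₂) − z·√(2p̄(1 − p̄)/n)] / √([p₁(1 − p₁) + p₂(1 − p₂)]/n)}

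- At 1%, OR .49: p₂ = .0049/.9949 = .004925. One-sided: (.005075 − 1.645 × .002023)/.002022 = .864, so power is .806.
- At 5%, OR .75: p₂ = .0375/.9875 = .037975. One-sided: (.012025 − 1.645 × .004820)/.004818 = .850, so power is .802.

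Solved for 80% power, the one-sided odds ratios are .494 and .751, matching .49 and .75. Two-sided they are .44 and .72, and none of the other two-sided formulas tried gave both stated values. The match uses all 7,241 students. The one-sided requirements are 7,112 (OR .49) and 7,190 (OR .75), so the margin is gone at 1 − 7,112/7,241 = 1.8% and 1 − 7,190/7,241 = 0.7% loss.

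**3. Counting only students with the outcome.** Retention is assumed. Sidedness is held fixed within each column.

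| Retention | Students with outcome | One-sided detectable OR, 1% / 5% | One-sided power at .49 / .75 | Two-sided detectable OR, 1% / 5% |
|---|---|---|---|---|
| 100% | 7,241 | .49 / .75 | .806 / .802 | .44 / .72 |
| 90% | 6,517 | .47 / .74 | .769 / .765 | .42 / .71 |
| 80% | 5,793 | .44 / .72 | .726 / .721 | .39 / .69 |
| 70% | 5,069 | .41 / .71 | .675 / .671 | .35 / .67 |

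The attrition effect is the change down a column. The gap between the one-sided and two-sided columns is a separate matter.

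Not every figure is this tight. The .88 at 50% incidence needs 6,062 students one-sided, so it tolerates about 16% loss (1 − 6,062/7,241).

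**4. When bias would arise.** Every input here is assumed. Let perpetration be 5% in both arms at post-test and at follow-up, so the true OR is 1.00. Let 40% of post-test perpetrators perpetrate again; the rate in the others is then (.05 − .05 × .40)/.95 = 3.16%.

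- READY to Stand arm: 50% of post-test perpetrators and 15% of the others are lost. Total loss is .05 × .50 + .95 × .15 = 16.75%.
- Wait-list arm: 25% and 16.3% are lost. Total loss is .05 × .25 + .95 × .163 = 16.75%.

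Observed follow-up prevalence is (.05 × .50 × .40 + .95 × .85 × .0316)/.8325 = 4.26% against (.05 × .75 × .40 + .95 × .837 × .0316)/.8325 = 4.82%, an OR of about .88. With 30% repeating instead of 40%, it is about .92. Overall attrition is identical in the two arms. If retention is instead the product of an arm factor and a post-test-status factor, the OR stays at exactly 1.00.

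**The case against.** **The model may not be a lone regression.** Step 4 is run as structural equation modelling, with latent constructs where possible, and is judged by RMSEA, SRMR and CFI. Those indices say little about a single logistic regression, so larger models are evidently meant for some outcomes. A joint model of post-test and follow-up would recover something. For a continuous outcome with wave correlation .5 and 20% missing follow-up, effective N is .80/(1 − .20 × .5²) = 84% of the full sample rather than 80%. This stands as a limit: the SAP leaves a joint model open. It does not write one down for binary outcomes, and a student with no post-baseline wave would still add essentially nothing on the treatment effect.

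**Baseline perpetration may already be adjusted for.** The propensity score draws on all pertinent confounders in Measurement Table 3, which is not among the documents. It therefore cannot be said that baseline answers are absent. Post-test answers cannot enter by that route.

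**The figures are provisional.** The SAP calls 1% to 5% conservative minimum rates and will recalculate power. Uncertainty about incidence moves the detectable OR from .49 to .75, far more than attrition does. This is fair, but the recalculation as written updates incidence only.

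**Stronger readings that the documents do not support.** A reader might infer that the effect estimate is biased by dropout. Analysing observed outcomes is valid if missingness depends only on variables in the model, and step 4 needed an interaction between arm and post-test perpetration. A reader might also set the two-sided values beside the stated .49 and .75 and blame attrition for the whole gap; at full N that gap is entirely sidedness.

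**Conclusion.** The point holds for the power basis and for the assurance that all enrolled cases are used, as applied to the binary outcomes in the model the SAP describes. For the primary outcome, the stated detectable odds ratios require essentially complete outcome data. Under assumed losses of 10 to 30%, one-sided power at those odds ratios is about .77 down to .67. The loss is moderate, and its true size is unknown because no attrition rate is given.

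Bias is a possibility to guard against. It arises if dropout depends on post-test perpetration differently in the two arms, and comparing overall attrition by arm, the check the SAP plans, would not reveal it.

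It would go too far to conclude that the trial is underpowered or that the SAP commits to a complete-case analysis. The final incidence and retention are unknown, and the structural equation wording leaves a joint model possible. The figures rest on 1:1 allocation, the normal approximation for two proportions, and no allowance for clustering or weighting.

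**What to change.** 1. Restate each Aim 2a minimum detectable effect at the number of students expected to have the outcome, showing 90, 80 and 70% retention and stating the sidedness of the test. Add expected retention to the power recalculation planned before Component B.
2. For binary outcomes, specify either a joint maximum likelihood model of post-test and follow-up with the baseline outcome, or multiple imputation by arm using baseline and post-test answers. Students seen at post-test but not at follow-up then contribute.
3. Limit the statement about all enrolled cases to what the chosen model delivers, and say that students with no post-baseline wave inform the propensity model but not, in any material way, the treatment effect.
4. Report attrition by arm within post-test perpetration status as well as overall.

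The cost is SAP wording, some extra modelling of a rare outcome, and a less favourable stated detectable effect. No extra students or visits are needed.

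### Aim 2a tests four to six secondary outcomes as effectiveness hypotheses, and nothing controls the error rate within that family

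*SAP*

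**What the plan says.** **Hypotheses.** SAP, Proposed Analyses, Outcome Analyses (Aim 2a), says that the effectiveness hypotheses cover CSEC perpetration as the primary outcome, followed by "reductions in CSEC victimization and TDV and SV victimization and perpetration and increases in bystander intervention in CSEC situations (secondary outcomes"). Of the resulting treatment contrasts it says: "These effects indicate whether the outcomes in the experimental condition differ significantly from those in the comparison condition".

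**Decision rule.** The end of the same section says: "We will evaluate our hypotheses across several indicators, including significance (p), confidence intervals, and the standardized difference between groups (d"), along with path direction and odds ratios. It gives no p-value threshold, testing order or adjustment.

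**Alpha.** The Aim 2a power section is introduced as "Power analyses to support the sample size for the effectiveness analyses for our primary, secondary, and intermediary outcomes". It sets power .80 and alpha .05 once for all of them and does not state sidedness.

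**Number of outcomes.** The power section writes TDV and SV together ("For secondary outcomes of TDV/SV perpetration and victimization, given past 12- months incidence rates"), which allows a count of four. It also powers six TDV sub-types ("For sub-types of TDV (past 12-month incidence rates: physical victimization: 18%; sexual victimization: 18%; psychological victimization: 66"%, and so on). The bystander outcome may be one measure or two ("For the secondary outcome CSEC bystander action and opportunity and intermediary outcomes").

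**Exploratory label.** The only impact analysis called exploratory is the pilot analysis of intermediary outcomes under Aim 1e. Neither document mentions multiplicity.

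**The concern.** A 5% error rate per test is not a 5% error rate for a family of tests. If the secondaries are read one by one at .05, the chance that an ineffective programme shows some significant secondary result is well above .05.

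This matters because the protocol's stated purpose is to evaluate RTS with a view to wide dissemination if it is judged effective. The primary outcome has no reliable incidence estimate. At the lowest assumed incidence, 1%, the SAP's own detectable odds ratio is .49, so a non-significant primary result is quite possible. Attention would then move to the secondaries, and the SAP does not say what they can support.

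**Working it through.** **1. Reproduce the SAP's figures.** Inputs from the SAP: N = 7,241, power .80, alpha .05, incidence 1% and 5%, stated detectable OR .49 and .75. Assumed: 1:1 allocation (the SAP gives about .5 for the pilot only) and independent students, so n = 7,241/2 = 3,620.5 per arm.

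p2 = [OR·p1/(1−p1)] / [1 + OR·p1/(1−p1)]

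power = Φ{ [|p1−p2|√n − z√(2p̄(1−p̄))] / √(p1(1−p1) + p2(1−p2)) }

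For p1 = .05 and OR = .75:
- p2 = .0380 and |p1−p2|√n = .724.
- One-sided (z = 1.645): power = Φ[(.724 − .477)/.290] = .80.
- Two-sided (z = 1.960): power = Φ[(.724 − .568)/.290] = .70.

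Solving for OR at power .80 gives .494 (1%) and .751 (5%) one-sided, and .440 and .722 two-sided. The stated .49 and .75 therefore fit a one-sided .05 test. Some other stated values do not: the .88 at 50% incidence is nearer the two-sided .877 than the one-sided .890. Sidedness has to be stated before any error rate is fully defined.

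**2. Family error rate at one time point, no RTS effect.** The documents give no correlation between outcomes, so a common correlation ρ is varied from 0 to .8.

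- Independent, either direction: 1 − .95^6 = .265 and 1 − .95^4 = .185.
- Independent, false benefit only (.025 each): 1 − .975^6 = .141 and 1 − .975^4 = .096.
- Correlated, either direction: 1 − ∫[Φ((c−√ρ·u)/√(1−ρ)) − Φ((−c−√ρ·u)/√(1−ρ))]^k φ(u)du, with c = 1.96. For false benefit the second Φ term is dropped.

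| ρ | 6 outcomes, either direction | 6, false benefit | 4 outcomes, either direction | 4, false benefit |
|---|---|---|---|---|
| 0 | 26.5% | 14.1% | 18.5% | 9.6% |
| .3 | 24.1% | 12.2% | 17.4% | 8.7% |
| .5 | 20.7% | 10.4% | 15.6% | 7.8% |
| .8 | 13.9% | 6.9% | 11.4% | 5.7% |

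The nominal rates are 5% (either direction) and 2.5% (false benefit). If the tests are one-sided at .05, false benefit is 12.6%-26.5% for six outcomes and 10.6%-18.5% for four, against a nominal 5%.

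**3. Two time points.** If significance at either post-test or follow-up counts, six outcomes become twelve two-sided tests. The rate is 46% if all are independent, 35% with both correlations (between outcomes and between times) at .5, and 21% with both at .8. If the same outcome must be significant in the same direction at both times, the rate with both at .5 is 4.6%. The SAP does not say which rule applies.

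**4. After adjustment.** Holm's first step for six outcomes uses .05/6 = .00833. The family rate, two-sided, is then 4.9% if independent and 4.1% at ρ = .5.

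**5. Detectable effect at that step, 5% incidence.** By the formula in step 1, OR moves from .75 to .68 (one-sided) or from .72 to .66 (two-sided).

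**The case against.** **Correlation.** No single error rate can be quoted. Figures such as 21% for one time point or 35% for two need a correlation of .5 that appears nowhere in the documents. This stands, so only the range is claimed.

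**Count.** A reader might infer at least six secondaries. The power section's pooled wording allows four, and the planned latent constructs may reduce the number further. This stands. The TDV sub-types are powered but not listed among the Aim 2a hypotheses, so they should not be counted as secondary tests.

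**Time points.** A reader might double the family for post-test and follow-up. The SAP sentence naming both is limited to continuous measures, its logistic models name no time point, and every secondary except the bystander outcome is powered through an incidence and odds ratio. The text could also be read as expecting significance at both times. The either-time rate is a possibility, not the plan's stated rule.

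**Hierarchy.** A reader might infer that there is none, or that a secondary may replace a null primary. One primary is clearly named, and no passage allows substitution. The gap lies within the secondary family and in what its results may support.

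**Threshold.** Alpha .05 is a power input, and hypotheses are to be judged on several indicators together. This is fair, but it is the only alpha given for Aim 2a and significance is one of the indicators.

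**Direction.** The either-direction rates include apparent harm. False benefit is about half as frequent. This also stands.

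None of these points brings the family rate down to its nominal level for one-time-point testing at .05.

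**Conclusion.** The point holds as a gap in the secondary family, not as a fault in the primary analysis. With four to six secondaries each tested two-sided at .05 at one time point, and correlations from .8 to 0, an ineffective RTS yields at least one significant secondary result about 11%-19% of the time (four outcomes) or 14%-26% (six). False benefit alone is about 6%-10% or 7%-14%, against 2.5%. The rates would be higher if continuous outcomes could be claimed at either time point.

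These figures assume equal correlations, approximately normal test statistics and the power section's alpha as the testing threshold. The documents do not support a single point value, a firm count of six, or the reading that the plan lets a secondary replace the primary.

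**What to change.** Add to Aim 2a, in words such as: CSEC perpetration is the single confirmatory outcome, tested at .05. The listed secondary outcomes form one family, tested with Holm's procedure at overall alpha .05. TDV sub-types and intermediary outcomes are exploratory. The text should also state how many secondary outcomes there are (TDV and SV pooled or separate, bystander as one measure or two), at which time point(s) they are tested, and whether tests are one- or two-sided.

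Alternatively, report the secondaries as estimates with confidence intervals and make no effectiveness claim from them. This costs no power.

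Either change is SAP wording and needs no new data. The cost of Holm is a less favourable detectable effect for the secondaries. At its strictest step for six outcomes, with 1:1 allocation and independent students, the detectable OR at 5% incidence moves from .75 to about .68 if one-sided, or from .72 to .66 if two-sided. The primary test is unaffected.
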